### Pivot Breath Sensor.

The primary endpoint will assess any change in the proportion of participants' Stage of Change response at day 28 compared to baseline

- A positive outcome is defined as a participant responding as more ready to quit. For example, a change in response from seriously thinking of quitting smoking "...within the next 6 months" at baseline to seriously thinking of quitting smoking "...within the next 30 days" at day 28.

The secondary endpoints include:

- The proportion of participants who reported  $\geq 1$  quit attempt by day 28; will be compared to zero
  - A quit attempt is defined as answering  $\geq 1$  to the following question: "Since you began using the Pivot Breath Sensor, how many times have you tried to quit smoking where you've gone at least 1 day without smoking a cigarette, even a single puff?"
- The proportion of participants who reduced their cigarettes per day (CPD) by  $\geq 50\%$  by day 28, compared to baseline

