## **6.6 SAMPLE SIZE AND JUSTIFICATION**

This study will enroll up to 220 participants. Consideration for the sample size included powering the study to observe a clinically meaningful change from baseline for the primary and secondary endpoints using 80% power at a statistical significance of  $P < 0.05$ . The primary endpoint utilized preliminary data from a similar 37 participant pilot study. Data at the 14-day time point showed 31%, 66% and 3% of participants had increased, unchanged and decreased Stage of Change, respectively, from baseline. To detect a statistically significant change in these proportions requires enrolling 50 participants.

The estimated proportion of participants achieving  $\geq 1$  quit attempt is 25% based on interim results from the pilot study. Based on the median prevalence of 65.4% for past-year quit attempts in the general population [13], the average monthly quit attempt rate is approximately 5%. To show that a proportion of 25% of participants making a quit attempt by day 28 is statistically different from 5% will require  $n=16$ .

Finally, literature indicates approximately 1% of the general population [14-18] and 2-5% of individuals in cigarette reduction studies [19, 20] will reduce their CPD by  $\geq 50\%$  on a monthly basis. Assuming that 10% of participants in the present study reduce their CPD by  $\geq 50\%$  by day 28, the present study will require  $n=185$  to show a difference from 5%. Taking these analyses into consideration along with expected attrition, the present study will enroll up to 220 participants.

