### **7.5 DAYS 1 THROUGH 84 – STUDY QUESTIONNAIRES**

Participants will receive periodic electronic questionnaires via email (Survey Monkey) that focus on attitudes towards quitting, smoking behavior, and participant feedback on breath sensor set-up, user experience, impact and commercialization (Section 7.7).

Participants will receive periodic reminders from study staff to complete the questionnaires via email, text or phone, as needed. All participants will receive the 28-day and 84-day questionnaires, regardless of previous completion of questionnaires.

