## 10.2 ANALYSIS

Changes in measurements from baseline will be assessed at different timepoints in the study. Participants will serve as their own controls and comparisons will be made to no change. One sample t-test will be used for numerical data. Fisher's Exact or Chi square tests will be used for categorical data. Analyses will be conducted to calculate mean (SD) for normally distributed variables for actual data or mean (SE) for modeled data and median (interquartile range) values in instances of non-normally distributed variables.

McNemar test will be used for 2-category match-paired data. Cohen kappa statistic will be used for 3-category match-paired data. To evaluate changes in attitudes or cigarettes smoked per day over time, repeated measures linear mixed model analyses will be performed using a compound symmetric correlation matrix to model the repeated measures within subjects. To make specific comparisons across time, F statistics will be computed using the results from the model. Statistical significance is set at  $P < .05$ .

Analyses for the outcomes will be evaluated for only those who complete the survey (i.e. completer) and assessed to take into account missing data. To be included in any completer analysis the participant must provide a baseline response and the outcome response. For outcomes that are missing data, these will be assessed pending the data type.

For categorical data, the last response post-baseline will be carried forward for the day 28 analysis and the last response post-28 days will be carried forward for the day 84 assessment. If there is not any data to carry forward, the data will be considered unchanged from baseline. Numerical data will use linear mixed modeling.

All deviations from the study protocol will be identified, recorded and analyzed.

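### As worded, the Day 84 missing-data rule in section 10.2 can reset a quit attempt already reported by Day 28 to its baseline value, and baseline is undefined for this outcome

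*Combined protocol and SAP*

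**What the plan says.** Section 10.2 plans a completer analysis and, beside it, an analysis that fills in missing data. For categorical data at Day 28, "the last response post-baseline will be carried forward for the day 28 analysis". At Day 84 the source is narrower: "the last response post-28 days will be carried forward for the day 84 assessment". With no source available, "If there is not any data to carry forward, the data will be considered unchanged from baseline". Numerical outcomes go elsewhere: "Numerical data will use linear mixed modeling".

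Section 6.3 defines a quit attempt by an answer of one or more to a question that begins "Since you began using the Pivot Breath Sensor, how many times have you tried to quit smoking". The named secondary endpoint is the proportion with at least one "quit attempt by day 28; will be compared to zero". Section 6.3 also lists quit attempts as a smoking-behavior outcome without limiting them to Day 28.

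The schedule in section 7.7 marks quit attempts at Registration and at Days 14, 28, 56 and 84. Section 8 lists two versions, one for the past 12 months and one for the study period. Section 7.5 adds: "All participants will receive the 28-day and 84-day questionnaires, regardless of previous completion of questionnaires".

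**The concern.** Whether someone has made at least one attempt since starting the sensor is a cumulative status. Once true, it stays true. The Day 84 rule treats it like an attitude item that can move back. It does not name responses up to Day 28 as a source, so Day 56 is the only scheduled answer that can fill a missing Day 84. If Day 56 is also missing, the participant returns to baseline, even though the study holds a record of the attempt and counted it at Day 28. No section exempts cumulative outcomes.

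The baseline value is itself unclear. No in-study attempt can exist before the sensor is used, yet the schedule collects a quit-attempt answer at Registration. The fallback could therefore mean zero, or it could mean a past-year answer. At stake is the imputed Day 84 quit-attempt result, which belongs to the outcomes that section 10.3 sends to the final report.

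**Working it through.** **The plan's own figure.** Section 6.6 expects 25% with an attempt, against a background for which "the average monthly quit attempt rate is approximately 5" percent, and states n = 16. The one-sample formula (normal approximation, two-sided 0.05, 80% power) gives

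n = [1.960 × √(0.05 × 0.95) + 0.842 × √(0.25 × 0.75)]² / 0.20² = 15.67, rounded up to 16.

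The figure is reproduced. It concerns Day 28 only, so the Day 84 rule does not touch it.

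**The rule applied to response patterns** (zero in-study attempts taken as baseline):

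| Attempt reported at | Missing | Day 28 value | Day 84 value |
|---|---|---|---|
| Day 28 | Days 56, 84 | attempt | no attempt |
| Day 14 only | Days 28, 56, 84 | attempt | no attempt |
| Days 28, 56 | Day 84 | attempt | attempt |
| Days 28, 84 | Day 56 | attempt | attempt |

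The reset needs Days 56 and 84 both missing. The second row does not depend on whether the Day 28 response counts as a source: that participant has no response at or after Day 28, is counted at Day 28 through carry-forward, and is reset at Day 84 either way.

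**Size if baseline is zero.** Let m be the share with no response after Day 28 (assumed 5-20%, since the plan gives no attrition rate) and r their attempt rate by Day 28. Recorded attempts lost = m × r.

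| m | r = 25% (plan) | r = 12.5% (assumed, half) |
|---|---|---|
| 5% | 1.25 points, 2.75 of 220 | 0.625 points, 1.4 of 220 |
| 10% | 2.5 points, 5.5 of 220 | 1.25 points, 2.75 of 220 |
| 20% | 5.0 points, 11 of 220 | 2.5 points, 5.5 of 220 |

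**Effect on the Day 84 total.** Assume that 5% per month of those without an attempt make one during the two months after Day 28. New attempts = 0.75 × (1 − 0.95²) = 7.31 points, so full follow-up would show 32.31%. Under the rule the total is (1 − m) × 32.31%. If recorded attempts are kept, add m × 25%.

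| m | Rule as worded | Recorded attempts kept |
|---|---|---|
| 5% | 30.70% | 31.95% |
| 10% | 29.08% | 31.58% |
| 20% | 25.85% | 30.85% |

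The total falls below the Day 28 value only if m exceeds 1 − 25/32.31 = 22.6%. At 2.5% per month, full follow-up would show 28.70% and the threshold is 12.9%. With no new attempts, any missingness lowers it.

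**Size if baseline is the past-12-month answer.** Section 6.6 cites 65.4% for past-year attempts in the general population. If that applied to the non-responders, the imputed total would exceed the total with recorded attempts kept by (65.4 − 25)% × m, which is 2.0 points at m = 5% and 8.1 points at m = 20%.

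**The case against.** The strongest reply is that no Day 84 yes/no analysis of quit attempts is spelled out. The named endpoints are all at Day 28, and the yes/no form is defined only there. The item asks for a count, and a count would go to the mixed model, where the carry-forward rule does not apply. The wording of the Day 56 and Day 84 items is not shown either. This stands as a limit: the point is conditional on a yes/no, since-start outcome. The study-period entry in section 8 supports that reading without proving it.

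Second, the comparison with zero in section 6.3 is the reference for a Day 28 proportion, not a participant's baseline value. This also stands. A reader might infer that the bias is always downward and so cannot flatter the device. The documents do not support that, because the fallback could be read as the past-year answer. That reading is less natural, but nothing rules it out.

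Third, Day 28 may have been meant as a permitted source. The text does not say so, and the parallel with the Day 28 rule, where baseline is the separate fallback and not a carried response, points the other way. Even on the generous reading, the participant who reported only at Day 14 is reset.

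Fourth, the missingness is assumed. Reminders, payment for questionnaires and the 14-day window for the final one all work against it. The gap between 185 and 220 in section 6.6 is 35/220 = 15.9%, which would imply about 25% × 15.9% = 4.0 points if all of that loss fell on Days 56 and 84 together. A reader might infer from section 7.5 that Day 56 may be withheld. That goes too far: section 6.2 schedules it for everyone, and section 7.5 merely leaves it out of its assurance.

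**Conclusion.** The point holds in a limited form. Section 10.2 as worded gives a wrong or undefined Day 84 value for a participant with a recorded attempt and no response after Day 28. Under the zero-baseline reading, 1.25-5.0 points of recorded attempts are lost (about 3-11 of 220). This rests on the plan's 25% applying to the non-responders and on an assumed 5-20% missing both later questionnaires; at half that attempt rate the loss is 0.6-2.5 points. Under the past-12-month reading the error could be upward.

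Three stronger readings are tempting and not supported:

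- **The trial's endpoints are compromised.** The primary and secondary endpoints are at Day 28, where any post-baseline response may be carried. The sample size and the completer analysis do not use the Day 84 rule.
- **The Day 84 proportion must fall below the Day 28 proportion.** That depends on new attempts; at 5% per month it takes more than 22.6% missing.
- **Missing Day 84 abstinence should be counted as smoking.** Assume 5-10% abstinent at Day 56, 5-20% then missing Day 84, 20-50% of the abstinent resuming and 1-5% of smokers newly abstinent. Carrying Day 56 forward then errs by −0.75 to +0.82 points, and counting missing as smoking errs by −0.17 to −2.50. Enrollees are daily smokers, so the existing fallback already counts those with no response after Day 28 as smoking.

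Priority is low: the affected result is a listed Day 84 outcome, not a named endpoint.

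**What to change.** Add to section 10.2:

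- For quit attempts since starting the sensor (yes/no), when the Day 84 response is missing, count the participant as having at least one attempt if the Day 14, 28 or 56 questionnaire reported one, and otherwise as having none.
- Do not use the past-12-month baseline answer for this imputation, and do not change any observed response.
- State whether the Day 28 response is among those that may be carried to Day 84.

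Keep the existing rule for the other categorical outcomes. Restricting the change to missing Day 84 values matters. A rule that made every reported attempt permanent could overwrite an observed answer of zero at Day 28 after a one at Day 14, and so alter a named secondary endpoint.

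The cost is a few lines of text and no new data. A small undercount remains, because unseen attempts after Day 28 count as none. At the assumed 5% per month this is m × 7.31 points, or 0.37-1.46 points for 5-20% missing.

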### 10.3 STUDY REPORT

A final study report will be produced at the end of the study; PowerPoint format is acceptable. The report will detail participant characteristics, breath sensor usage, the aforementioned outcomes of changes in attitudes towards quitting and smoking behavior as well as participant feedback.

### 10.4 DEVIATIONS FROM PROTOCOL

To be determined by the study team during the study. Deviations will be assessed through a consensus review of the study team. All deviations will be identified, recorded and analyzed in the final report.

### 10.5 RECORD RETENTION

Record keeping is performed in accordance with the SOP Control of Quality Records, [REDACTED]

## 11. CONFLICTS OF INTEREST

The following conflicts of interest are noted:

- The study sponsor is Carrot Inc., [REDACTED]
- The principal investigator and co-investigators own equity in Carrot Inc., which is the company that invented and owns the Pivot Breath Sensor, which is being evaluated in this study.
- The company (Carrot Inc.) holds patent rights to one of the devices being evaluated in the study (the Pivot Breath Sensor).

The investigator [REDACTED] holds a position of senior management officer, as Sr. Director of Clinical and Medical Affairs. The Co-Investigator [REDACTED] holds a position of Director of Clinical Affairs. The Co-Investigator [REDACTED] holds a position of Senior Clinical Research Associate. These conflicts of interest are mitigated by the following:

- The risk profile of the study, specifically, that there are minimal anticipated risks or harms to the subject. No medical decisions are made based on study data. The process of setting up the Pivot Breath Sensor and providing breath samples is non-invasive, and participants have access to trained study and customer support personnel for assistance as needed. Breath samples are done at the discretion of the study participant.
- The role of Carrot Inc. in the study is outlined in the study Informed Consent Form; participants will be aware of this role prior to providing informed consent.
- The aim of the study is to assess the performance of the Pivot Breath Sensor in intended

Rev. A Original Protocol

Rev. B Added the following text to section 10.1 “Data Collection and Confidentiality” regarding the maximum time data will be retained: “The data shall be retained for a maximum period of time that is equivalent to the design and expected life of the Pivot Breath Sensor device or the duration of the study sponsor's (Carrot Inc.) existence, whichever is the shortest of the two.” Section 2.3 “Potential Risks and Benefits” was updated to include possible risks of data breach and participant anxiety associated with using the Pivot Breath Sensor multiple times a day.
